#### 3.1.3. Vital Signs

Supine blood pressure, pulse rate, temperature and respiratory rate will be measured at times specified in the SoA given in the protocol.

The baseline will be the last pre-dose measurement.

#### 3.1.4. ECG

Standard 12 lead ECGs should be collected at times specified in the SoA section of the protocol using an ECG machine that automatically calculates the HR and measures PR interval, QT interval, QTcF, and QRS complex.

Triplicate 12 lead ECGs will be obtained approximately 2 to 4 minutes apart during clinical confinement; the average of three triplicate ECG measurements collected at Day 1 predose will serve as each participant's time controlled baseline QTcF value. This baseline definition will be applied to other ECG parameters.

# 3.2. Secondary Endpoint(s)

#### 3.2.1. Pharmacokinetic Endpoints

- PF-07261271 PK parameters as data permit:
  - Part A (SAD-IV or SC Infusion Dosing): AUClast, AUCinf, Cmax, Tmax, and t/2;
  - Part B (MD-IV or SC Dosing) or MD cohorts: AUCtau, Cmax, Tmax, and t/4.

The PK parameters to be assessed, their definition, and method of determination are detailed in Table 2. Actual PK sampling times will be used in the derivation of PK parameters. Some of these PK parameters are exploratory endpoints and are described in Section 3.3.

Table 2. Serum PK Parameters

Parameter	Definition	Method of Determination
Part A: SAD		
AUClast	Area under the concentration-time curve from time 0 to the time of the last quantifiable concentration (C last ).	Linear/Log trapezoidal method
COL		
AUC inf a	Area under the serum concentration time-profile from time 0 extrapolated to infinite time	AUC last + (C last */k el ), where C last * is the predicted serum concentration at the last quantifiable time point estimated from the log-linear regression analysis
CCI	ė.	
Cmax	Maximum serum concentration	Observed directly from data
CCI		

Table 2. Serum PK Parameters

Parameter		Definition M		Method of Determination
T max	Tim	e for C max	r C max Observed occurrence	
t % a	Terr	rate or regret time-		kel, where kel is the terminal phase stant calculated by a linear on of the loglinear -concentration rve. Only those data points judged be the terminal log-linear decline sed in the regression
CL/F and CCI	(CL	arent clearance for SC dosing F) and systemic clearance for osing (CL)	nt clearance for SC dosing Dose/AUC inf and systemic clearance for	
$V_{ss}^{a}$		me of distribution at steady (IV dosing)	CL×MR	Т
V z /F a		arent volume of distribution ng the terminal phase (SC ng)		
MRTª	RT a Mean residence time		AUMC inf /AUC inf , where AUMC inf is the area under the first moment curve from time zero to infinity.	
Part B: MD	(4)	W:	2	
Parameter	Study Day Relative to Day 1	Relative to		Method of Determination
AUCtau	1, CC	Area under the concentra profile from time zero to (τ), the dosing interval, v tau=672 hours for Q4W	time tau vhere	Linear/Log trapezoidal method
CCI				20.
C max	1,CCI	Maximum serum concen	tration.	Observed directly from the data
77.00	1, CCI	Time for C max .	Time for C max .	
T max	1, CCI	Time for C max .		Observed directly from data

Table 2. Serum PK Parameters

Para	ameter	Definition	Method of Determination
t % a	CCI	Terminal elimination half-life.	Log e (2)/k el , where k el is the terminal phase rate constant calculated by a linear regression of the loglinear-concentration time-curve. Only those data points judged to describe the terminal log-linear decline will be used in the regression

If data permits.

# 3.2.2. Immunogenicity

 Incidence of the development of ADA and, if appropriate, NAb against PF-07261271 following single and multiple doses.

## 3.3. Tertiary/Exploratory Endpoint(s)

PF-07261271 PK parameters, as data permit:

The PK parameters to be assessed, their definition, and method of determination are detailed in Table 2.

- CCI
- Change from baseline in blood levels of exploratory PD biomarkers:
  - Serum proteins.

    CCI

The baseline will be the last pre-dose measurement.

#### 4. ANALYSIS SETS (POPULATIONS FOR ANALYSIS)

Data for all participants will be assessed to determine if participants meet the criteria for inclusion in each analysis population prior to unblinding and releasing the database and classifications will be documented per standard operating procedures.

Participant Analysis Set	Description	Applicable Analysis (for additional information refer to Section 6)
Enrolled	"Enrolled" means a participant's, or their legally authorized representative's, agreement to participate in a clinical study following completion of the informed consent process and randomization/assignment to study intervention. A participant will be considered enrolled if the informed consent is not withdrawn prior to participating in any study activity after screening. Potential participants who are screened for the purpose of determining eligibility for the study, but do not participate in the study, are not considered enrolled, unless otherwise specified by the protocol.	
Full analysis set	All participants randomly assigned to study intervention and who take at least 1 dose of study intervention.	
Safety analysis set	All participants randomly assigned to study intervention and who take at least 1 dose of study intervention. Participants will be analyzed according to the product they actually received.	
PK population	The PK concentration population will be defined as all randomized participants who received at least 1 dose of PF-07261271 and in whom at least 1 serum concentration value is reported.	
PK parameters  The PK parameter analysis population will be defined as all randomized participants who received at least 1 dose of PF-07261271 and who have at least 1 of the PK parameters of interest calculated.		PK analysis
PD analysis set	All randomized participants who received at least 1 dose of PF-07261271 and who have baseline and at least 1 post-dose assessment.	PD analysis

#### 4.1. Treatment Misallocations

All analyses will be performed on an "as-treated" basis and will not include data from participants who are randomized but not treated.

If a participant takes a treatment that is not consistent with the treatment they are randomized to, then they will be reported under the treatment that they actually receive for all safety, PK and pharmacodynamic analyses, where applicable.

#### 4.2. Protocol Deviations

Participants who experience events that may affect their PK profile may be excluded from the PK analysis. At the discretion of the pharmacokineticist, a concentration value may also be excluded if the deviation in sampling time is of sufficient concern or if the concentration is anomalous for any other reason.

A full list of protocol deviations will be compiled and reviewed prior to database closure.

#### 5. GENERAL METHODOLOGY AND CONVENTIONS

## 5.1. Hypotheses and Decision Rules

No formal hypothesis testing will be performed in this study.

### 5.2. General Methods

Descriptive analyses will be performed. Some measures will be summarized using graphical representations, where appropriate.

#### 5.2.1. Analyses for Continuous Endpoints

For continuous variables, the data will be summarized using the number of participants, mean, median, standard deviation, minimum, and maximum in accordance with current Pfizer's data and reporting standards. For appropriate PK parameters, geometric mean and geometric coefficient of variation (geocv%) will also be summarized.

#### 5.2.2. Analyses for Categorical Endpoints

For categorical or ordinal variables, number of participants, numbers and percentages of participants meeting the categorical criteria will be supplied in accordance with current Pfizer's data and reporting standards.

#### 5.3. Methods to Manage Missing Data

For the analysis of safety endpoints, the sponsor data standard rules for imputation will be applied.

Methods to handle missing PK data are described below.

## Concentrations Below the Limit of Quantification:

In all data presentations (except listings), concentrations below the limit of quantification (BLQ) will be set to zero. (In listings BLQ values will be reported as "<LLQ" where LLQ will be replaced with the value for the lower limit of quantification).

#### Deviations, Missing Concentrations and Anomalous Values:

In summary tables and plots of median profiles, statistics will be calculated having set concentrations to missing if 1 of the following cases is true:

- A concentration has been collected as ND (ie, not done) or NS (ie, no sample).
- A deviation in sampling time is of sufficient concern or a concentration has been flagged anomalous by the pharmacokineticist.

Note that summary statistics will not be presented at a particular time point if more than 50% of the data are missing.

#### Pharmacokinetic Parameters:

Actual PK sampling times will be used in the derivation of PK parameters. If a PK parameter cannot be derived from a participant's concentration data, the parameter will be coded as NC (ie, not calculated). (Note that NC values will not be generated beyond the day that a participant discontinues). In summary tables, statistics will be calculated by setting NC values to missing; and statistics will be presented for a particular dose with ≥3 evaluable measurements.

If an individual participant has a known biased estimate of a PK parameter (due for example to an unexpected event such as vomiting before all the compound is adequately absorbed from the gastrointestinal tract), this will be footnoted in summary tables and will not be included in the calculation of summary statistics or statistical analyses.

#### 6. ANALYSES AND SUMMARIES

#### 6.1. Primary Endpoint(s): Safety Summaries and Analyses

The safety data will be summarized in accordance with Pfizer Data Standards. All participants who receive at least 1 dose of study intervention (safety population) will be included in the safety analyses. All safety data will be summarized descriptively through appropriate data tabulations, descriptive statistics, categorical summaries, and graphical presentations. Safety endpoints for the study include:

- TEAEs and SAEs;
- Withdrawals from active treatment due to AEs;

- Serious infections, defined as any infection (viral, bacterial, and fungal) requiring hospitalization or parenteral antimicrobials;
- Safety laboratory tests (eg, hematology [including coagulation panel], chemistry and urinalysis);
- ECG (HR, QT, QTc, PR, and QRS intervals) changes from baseline;
- Vital signs (BP, pulse rate and temperature).

Changes from baseline on laboratory data and vital signs will be additionally summarized. Participant listings will also be produced for these safety endpoints.

AEs, ECGs, BP, pulse rate, temperature, and safety laboratory data will be reviewed and summarized on an ongoing basis during the study to evaluate the safety of participants. Any clinical laboratory, ECG, BP, and pulse rate abnormalities of potential clinical concern will be described. Safety data will be presented in tabular and/or graphical format and summarized descriptively, where appropriate.

Medical history and physical examination and neurological examination information, as applicable, collected during the course of the study will be considered source data and will not be required to be reported, unless otherwise noted. However, any untoward findings identified on physical and/or neurological examinations conducted during the active collection period will be captured as AEs, if those findings meet the definition of an AE. Data collected at screening that are used for inclusion/exclusion criteria, such as laboratory data, ECGs, and vital signs, will be considered source data, and will not be required to be reported, unless otherwise noted. Demographic data collected at screening will be reported.

## 6.1.1. Adverse Events

Adverse events will be reported in accordance with the sponsor reporting standards.

Participant discontinuations due to adverse events will be detailed by treatment. Data will be reported in accordance with sponsor reporting standards.

Injection site reaction (ISR) and infusion related reaction (IRR) categories will not be summarized under adverse events reporting (see Section 6.1.2 and Section 6.1.3 for details).

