8.3.7. Infusion and Injection Site Reaction and Anaphylaxis Assessment

Participants will be monitored for signs of any infusion or injection site reactions, including but not limited to erythema, swelling, bruising, pain, or pruritus at times specified in the SoA.

Any signs or symptoms related to either an infusion or injection site reaction should be treated according to the investigator's standard of care and reported as AEs. All anaphylactic reactions will be assessed by the Pfizer clinical team according to Sampson's criteria (Appendix 9).

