# 3. ENDPOINTS AND BASELINE VARIABLES: DEFINITIONS AND CONVENTIONS

#### 3.1. Primary Endpoint(s): Safety Endpoints

The primary endpoints include:

- Incidence and severity of TEAEs, SAEs.
- Change from baseline in vital signs (BP, PR, and temperature measurements).
- Change from baseline in clinical laboratory values (chemistry and hematology including coagulation panel).

Change from baseline in ECG parameters (heart rate, QT, QTc, PR, and QRS intervals).

The following data are considered in standard safety summaries (see protocol for collection days, baseline assessment, and list of parameters):

- AEs;
- Safety laboratory tests;
- Vital signs (BP, PR, and temperature measurements);
- ECG.

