#### 3.1.1. Adverse Events

An adverse event (AE) is considered a Treatment-Emergent Adverse Event (TEAE) if the event started during the effective duration of treatment. All events that start on or after the first dosing day and time/start time, if collected, but before the end of the last follow-up date, will be flagged as TEAEs. The algorithm will not consider any events that started prior to the first dose date. If an AE starts on the same day as the first dose date, it will be considered treatment emergent unless the CRF data indicates otherwise via explicitly recording time for AE onset which was occurred before the first treatment dosing.

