#### 6.1.2. Immune-based AEs

Immune-based adverse events will be summarized by visits. If ADA results are available, immune-based adverse events may be summarized by categories of ADA results (for example, by ADA positive, negative and not-tested categories). Immune-based adverse events will include ISR and IRR, and clinically evaluated results of anaphylaxis based on the Sampson's Criteria, and AEs based on the Anaphylactic Reaction Standardised MedDRA Query (SMQ), Angioedema SMQ, Hypersensitivity SMQ, cytokine storm, and delayed immune response.

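### Read literally, SAP 6.1.1 leaves injection-site and infusion-related reactions out of the overall TEAE tables; the SAP should say whether they count

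*SAP*

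**What the plan says.** - **Primary endpoint.** SAP 3.1 lists "Incidence and severity of TEAEs, SAEs" first among the primary endpoints, with no class of event set aside. Protocol Section 3 has the same endpoint.
- **TEAE definition.** SAP 3.1.1 flags as treatment-emergent "All events that start on or after the first dosing day and time/start time", up to the last follow-up. It makes no exception for local or infusion reactions.
- **Status of the reactions.** Protocol 8.3.7 says that signs or symptoms of either an infusion or an "injection site reaction should be treated according to the investigator's standard of care and reported as AEs".
- **The sentence at issue.** SAP 6.1.1: "Injection site reaction (ISR) and infusion related reaction (IRR) categories will not be summarized under adverse events reporting". It points to 6.1.2 and 6.1.3 for details.
- **Where they go.** SAP 6.1.2 says "Immune-based adverse events will include ISR and IRR", together with anaphylaxis by Sampson's criteria, three standardised MedDRA queries, cytokine storm and delayed immune response. On layout, "Immune-based adverse events will be summarized by visits", with an optional split by ADA result. Section 6.1.3 is Laboratory Data and does not mention reactions.
- **General rules that also apply.** For categorical data, SAP 5.2.2 says that "numbers and percentages of participants meeting the categorical criteria will be supplied". For the safety analysis set, SAP 4 says "Participants will be analyzed according to the product they actually received". SAP 6.1 plans participant listings and defers layouts to the sponsor's data standards.
- **Declared changes.** The entry under SAP 2.1, on modifications to the protocol's analysis, is that none apply. The SAP version history records a change to Section 6.4 only.

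**The concern.** A reaction that starts after the first dose is an AE under Protocol 8.3.7 and a TEAE under SAP 3.1.1. It therefore belongs in the primary endpoint. The sentence in 6.1.1, followed as written, has a programmer leave it out of the AE summaries. The table headed as overall TEAE incidence would then count something narrower than the endpoint, with nothing in SAP 2.1 to tell the reader so.

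The class of event is not incidental. Protocol 2.3.1 names anaphylaxis, infusion reactions and injection site reactions as a potential risk. Protocol 4.2 gives safety signals related to SC dosing as one reason for the optional multiple-dose cohort. No hypothesis is tested, so these descriptive tables are the primary result.

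The separate table in 6.1.2 does not make up for this. Even a complete reaction table cannot be added to a TEAE table that omits reactions, because the reader cannot see which participants appear in both.

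**Working it through.** **Step 1. Group sizes (Protocol 4.1.1 and 4.1.2), checked against the plan's totals.** Active + placebo: Cohorts 1 and 2, 2+2 each; Cohort 3, 4+2; Cohorts 4, 5, 6 and 7, 6+2 each; Cohort 8, 4+1.
- Cohorts 1 to 5: 4+4+6+8+8 = 30.
- Adding Cohorts 6, 7 and 8: 30+8+8+5 = 51.

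Both match Protocol 9.5.

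**Step 2. The two readings side by side.**

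| | Literal reading | Milder reading |
|---|---|---|
| What 6.1.1 withholds from AE tables | The reaction events | Only grouped rows or displays |
| Overall TEAE count | Omits these events | Unchanged |
| Agreement with SAP 3.1.1, Protocol 8.3.7 and the primary endpoint | Conflicts | Agrees |
| Agreement with SAP 2.1 (no modification) | Conflicts | Agrees |

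The word 'categories' supports the milder reading. One feature supports the literal one: 6.1.2 also groups anaphylaxis, angioedema and hypersensitivity events, yet 6.1.1 withholds only injection-site and infusion reactions from AE reporting. No sentence settles the matter.

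**Step 3. Size on the literal reading.** Let n be the arm size and k the number of participants in that arm whose only TEAE is such a reaction. Displayed TEAE incidence falls by k/n. The documents give no reaction rate, so k is unknown; k = 0 gives no change. For illustration, with k = 1:
- n = 6 (active, Cohorts 4 to 7): 1/6 = 16.7 points
- n = 4 (active, Cohorts 3 and 8): 1/4 = 25 points
- n = 2 (active, Cohorts 1 and 2; placebo, Cohorts 1 to 7): 1/2 = 50 points

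The direction of the active-minus-placebo difference is not fixed. In Cohort 5 the change is −(k active)/6 + (k placebo)/2. One such active participant gives −16.7 points; one such placebo participant gives +50 points.

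**Step 4. Can the by-visit table supply the any-time incidence?** SAP 5.2.2 implies numbers and percentages of participants, and SAP 4 and 4.1 imply presentation by treatment received. Suppose a of 6 active participants react after the first dose and b of 6 after the second (assumed counts). Any-time incidence lies between max(a, b)/6 and min(a+b, 6)/6.
- a = b = 2: 2/6 to 4/6, that is 33.3% to 66.7%
- a = b = 3: 3/6 to 6/6, that is 50% to 100%

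By-visit percentages alone therefore do not fix any-time incidence.

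**Step 5. Are the data there?** Yes. Protocol Appendix 3 (10.3.3) has the investigator grade intensity for every AE, and SAP 6.1 plans listings. The omission would be in the summary, not in collection.

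**The case against.** The best defence is that the literal reading sets one sentence against the rest of the SAP. SAP 3.1.1 flags every post-dose event, 6.1 promises that all safety data will be summarized, and 2.1 says nothing was modified. The last can as easily mean that no exclusion was intended. Protocol 8.3.7 has individual signs and symptoms reported as AEs, so the separate terms may enter the TEAE tables whatever happens to a grouped category. This stands as a plausible reading, and under it the effect on TEAE counts is zero. It does not remove the ambiguity: two programmers could build different primary tables from the same sentence.

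Two stronger inferences are tempting, and the documents do not support either.
- A reader might infer that the reactions drop out of primary-endpoint reporting altogether. They do not. Section 6.1.2 sits under 6.1, the primary-endpoint section, so the reactions move to another summary there and are also listed.
- A reader might infer that 6.1.2 is singled out by its silence on any-time incidence and severity. It is not. Section 6.1.1 gives no such layout for any AE and defers to sponsor standards that are not in the documents. Those standards may supply both for 6.1.2 as well.

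It is also fair to say that the percentages above are 1/n arithmetic on assumed counts, and that small arms make any single event look large. AE monitoring is scheduled out to Day 451 or Day 471, subject to the final follow-up visit, which gives ample time for other TEAEs, so k may well be zero. Dose-escalation stopping under Protocol 6.6.1 rests on event-level criteria and not on the final TEAE table; no decision has been shown to change.

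**Conclusion.** The point holds as a conflict on the literal reading and an unresolved ambiguity otherwise. As written, SAP 6.1.1 can produce overall TEAE incidence and severity tables that omit events the SAP itself defines as TEAEs, with no modification declared. Whether it will do so depends on what 'categories' means, which the SAP leaves open.

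The size is k/n per arm and cannot be estimated from the documents. It is zero if k = 0 or if only grouped displays move; one affected participant in an arm of 6 is 16.7 points. This rests on the protocol's planned arm sizes and on the sponsor's unseen standards not overriding the study-specific sentence. The reactions remain tabulated in 6.1.2 and listed, so the issue is the completeness of the primary table and not loss of data. It is worth correcting because the correction is small. Whether an intended exclusion would be major enough to need a protocol amendment under Protocol Section 9 is a judgment that the documents do not settle.

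**What to change.** 1. In SAP 6.1.1, replace the sentence with: *ISR and IRR events are counted in the overall TEAE incidence and severity summaries by treatment; they are additionally summarized as immune-based AEs in Section 6.1.2.*
2. In SAP 6.1.2, keep the by-visit summary and add, by treatment, the number and percentage of participants with at least one event and their maximum severity.
3. If exclusion from the TEAE tables is truly intended, declare it in SAP 2.1 and footnote those tables.
4. Delete the pointer to 6.1.3 (clerical).

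The cost is SAP wording and one table layout. No new data are needed.

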#### 6.1.2. Immune-based AEs

Immune-based adverse events will be summarized by visits. If ADA results are available, immune-based adverse events may be summarized by categories of ADA results (for example, by ADA positive, negative and not-tested categories). Immune-based adverse events will include ISR and IRR, and clinically evaluated results of anaphylaxis based on the Sampson's Criteria, and AEs based on the Anaphylactic Reaction Standardised MedDRA Query (SMQ), Angioedema SMQ, Hypersensitivity SMQ, cytokine storm, and delayed immune response.

